6 SUBJECT SELECTION

6.1 Study Population

120 MSM cis-gender males who binge drink who meet the inclusion and exclusion criteria will be eligible for participation in this study.

6.2 Inclusion Criteria

- (1) Male gender;
- (2) self-reported anal sex with men in the prior three months while under the influence of alcohol;
- (3) at least one binge drinking (five or more drinks on a single occasion) session per week in the prior three months;
- (4) interested in reducing binge alcohol consumption;
- (5) HIV-negative by rapid antibody test or medical record documentation of HIV infection (HIV positive participants);
- (6) no current acute illnesses requiring prolonged medical care;
- (7) no chronic illnesses that are likely to progress clinically during trial participation;
- (8) able and willing to provide informed consent and adhere to visit schedule;
- (9) age 18-70 years;
- (10) baseline CBC, total protein, albumin, glucose, alkaline phosphatase, creatinine, BUN, and electrolytes without clinically significant abnormalities as determined by study clinician in conjunction with symptoms, physical exam, and medical history.
- (11) Written informed consent (and assent when applicable) obtained from subject or subject's legal representative and ability for subject to comply with the requirements of the study.

6.3 Exclusion Criteria

- (1) Any psychiatric (e.g. depression with suicidal ideation) or medical condition that would preclude safe participation in the study;
- (2) known allergy/previous adverse reaction to naltrexone;
- (3) current use of/ dependence on any opioids or a known medical condition which currently requires/may likely require opioid analgesics;
- (4) opioid-positive urine at enrollment;
- (5) current CD4 count < 200 cells/mm³;

- (6) moderate/severe liver disease (AST, ALT \geq 3 times upper limit of normal);
- (7) impaired renal function (creatinine clearance $<$ 50 ml/min);
- (8) currently participating in another intervention research study with potential overlap;
- (9) alcohol dependence as determined by SCID criteria (participants with non-dependent alcohol use disorders/symptoms of alcohol abuse [per DSM-IV] are *eligible*)
- (10) any condition that, in the principal investigator and/or study clinician's judgment interferes with safe study participation or adherence to study procedures;
- (11) not having a cell-phone that can send and receive text messages;

7 CONCURRENT MEDICATIONS

All subjects should be maintained on the same medications throughout the entire study period, as medically feasible, with no introduction of new chronic therapies.

7.1 Allowed Medications and Treatments

Standard therapy is allowed except for naltrexone treatments and opioid medications as noted in the exclusion criteria described above and as noted in the prohibited medications section below.

Prohibited Medications and Treatments

The following medications are prohibited during the study and administration will be considered a protocol violation:

- 1) Opioid medications
- 2) Naltrexone treatments

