within one hour of oral administration. The mean elimination half-life for naltrexone and 6-β-naltrexol are four and 13 hours, respectively.⁷¹ Naltrexone also has high affinity to the μ-opioid receptor ($K_i = 2.5 \pm 0.21$ nM) and a single 50 mg dose can block μ-opioid receptors for up to 72 hours⁷⁵ raising the possibility that dosing even 1-2 days prior to anticipated alcohol consumption may be effective. **Targeted administration of naltrexone on an “as needed” basis has shown promise in reducing heavy drinking among heterosexuals.** Targeted naltrexone dosing was feasible and acceptable in a small pilot study of heavy-drinking young adults not ready or willing to abstain from alcohol; the trial completion and targeted medication adherence rates were 93% and 83%, respectively.⁷⁶ Other samples of non-dependent heavy drinkers have also been successfully recruited and retained in targeted dosing studies.^{11, 77-79} Targeted naltrexone administered after a period of daily dosing significantly reduced heavy-drinking relapse.⁸⁰ Similarly, in a trial conducted by Kranzler, et al., men assigned to targeted naltrexone showed significant reductions in mean drinks per day, and in number of drinks during drinking days, compared to those assigned to *daily* naltrexone administration, *daily* placebo, or targeted placebo.¹¹ Intermittent dosing schedules for opioid antagonists like naltrexone show similar results: targeted nalmefene reduced heavy drinking days, “very heavy” drinking days, and number of drinks during drinking days in randomized controlled trials.^{81, 82} None of these studies have evaluated sexual risk behaviors or exclusively recruited binge drinking MSM at risk for acquiring or transmitting HIV. **Questions about the efficacy of targeted naltrexone to reduce alcohol-related sexual risk behavior remain unanswered; no efficacy trial has determined if targeted use of pharmacologic agents for binge drinking can reduce HIV risk behavior.**

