A review of the literature concluded that in patients treated for heroin or alcohol dependence, naltrexone does not cause clinically significant liver disease or exacerbate pre-existing liver disease.⁷¹ However, naltrexone has the capacity to cause hepatocellular injury in excessive doses and is contraindicated in acute hepatitis and liver failure.⁶⁹ Patients with these conditions will be excluded from our trial. Naltrexone is also contraindicated in patients who are currently dependent on opioids or in acute opioid withdrawal. The team anticipates that few participants will be excluded by virtue of current opioid use; for example, in our recently published mirtazapine study, only 7% of MSM met criteria for opioid dependence. Although the opioid blockade produced by naltrexone is surmountable, this situation requires careful medical management by trained personnel in settings equipped for resuscitation. Attempts by patients to overcome naltrexone's opioid antagonism may lead to an overdose. Naltrexone may also precipitate severe opiate withdrawal, including mental status change, nausea, vomiting, diarrhea, and dehydration in patients who are not opioid-free for a minimum of 7 to 10 days.⁶⁹ For this reason, urine opioid testing is needed to screen all potential participants for opioid use. Patients who have a foreseeable need for opioid pain management (e.g. potential elective surgery in the study period) will also be excluded. Additionally, all patients will be fully informed verbally and in the written consent form about the potential for overdose by attempting to overcome naltrexone's opioid antagonism.

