8.4.1 Dosage/Dosage Regimen

The dose of naltrexone being investigated for potential as a pharmacotherapeutic on an as-needed basis to reduce binge drinking is 50 mg. It is recommended participants take one capsule of medication by mouth 1 to 2 hours before starting an episode of binge drinking. Participants will be instructed to take no more than one capsule in a 24-hour period. No adjustments for weight, age, or meals is required. The dose of naltrexone being investigated for potential as a pharmacotherapeutic on an as-needed basis to reduce binge drinking is 50 mg. It is recommended participants take one capsule of medication by mouth 1 to 2 hours before starting an episode of binge drinking. Participants will be instructed to take no more than one capsule in a 24-hour period. No adjustments for weight, age, or meals is required.

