8.4.2 Dispensing

Study medications will be dispensed by the study clinician (licensed medical practitioner) in treatment bottles that are labeled with the study drug number, principal investigator name, prescribing physician name (medical director), required FDA warning statement, emergency pager number, directions for participant use and storage, and lot and expiration information.

Further, at time of study drug dispensing, the study clinician will review with the participant how to take the study medication, possible side effects they may encounter, and how to access the study clinician by emergency pager if necessary. The study clinician will also answer any questions the participant might have.

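### No visible on-treatment rule holds study drug after opioid use or an opioid-positive urine, or says when it may restart

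*Combined protocol and SAP*

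**What the plan says.** **The hazard.** Section 2.1 says naltrexone may cause severe withdrawal "in patients who are not opioid-free for a minimum of 7 to 10 days". It draws the consequence for entry: "urine opioid testing is needed to screen all potential participants for opioid use".

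**Entry.** Section 6.3 excludes current opioid use or dependence, likely need for opioid analgesics (criterion 3) and "opioid-positive urine at enrollment" (criterion 4). Section 9.1.6 documents medications from 30 days before enrollment onward.

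**On treatment.** Section 7.1 lists opioid medications under "The following medications are prohibited during the study and administration will be considered a protocol violation", and Section 13 gives their use as an example of a violation. Sections 9.3.5.1 and 10.4 provide weekly urine testing for opioids, with laboratory confirmation of positives. Section 10.4 also offers a weekly talk with the doctor or nurse about medication changes where needed. Men receive a wallet card, an emergency pager number and a dispenser that carries warnings about combining drugs (8.4.2, 8.4.3, 8.6). Sections 12.1 and 13 let the investigator or PI stop treatment or withdraw a man.

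**Dosing.** Capsules are self-administered as needed. Section 8.4.3 encourages at least 3 a week from a supply of 28 a month. Section 8.4.1 sets the ceiling: "Participants will be instructed to take no more than one capsule in a 24-hour period".

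**The concern.** The plan detects opioid use on treatment and labels it, but does not say what happens to the study drug. The hazard in Section 2.1 arises from taking naltrexone too soon after an opioid, so the protective step is to withhold the next capsules. A violation form and a later decision about withdrawal do not do that, and neither does sending the urine for confirmation.

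Doses are taken at home between visits. A man given an opioid analgesic midweek could take his next capsule before any staff member knows. A man with a positive cup could leave the visit with his existing supply, and with more if he needs it, while confirmation is pending. At stake is participant safety in the naltrexone arm, not the validity of the primary comparison.

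**Working it through.** There is no stated figure to reproduce. The check has two parts.

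**1. What each on-treatment provision does, and what it leaves open**

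| Section | What it provides | What it leaves open |
|---|---|---|
| 7.1, 13 | Opioids prohibited; use is a violation; PI decides on withdrawal | Whether capsules stop meanwhile; when they may resume |
| 9.3.5.1 | Weekly cup; positives confirmed by the laboratory | Dosing while confirmation is pending, and after it |
| 10.4 | Urine collected; talk about medication changes where needed; further supply where needed | Dispensing is not conditional on the cup result |
| 12.1 | Treatment may be stopped for a violation or an adverse event | A possible reason to stop, not a required hold; no restart condition |
| 8.4.3 | Training on timing, daily limit, not sharing, wallet card | No visible instruction to skip a capsule after an opioid |

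The overdose warning in Section 2.1 covers the reverse case, taking opioids to overcome the blockade.

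**2. Size of the exposure if nothing is held**

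Inputs: interval of 7 to 10 days (2.1); at least 3 capsules a week encouraged and 28 supplied a month (8.4.3); at most one per 24 hours (8.4.1); tests 7 days apart (9.3.5.1). The dosing patterns are assumptions.

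Capsules inside the interval = capsules per week × days / 7.

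- One a week: 1 × 7/7 = 1.0 to 1 × 10/7 = 1.4.
- Three a week: 3 × 7/7 = 3.0 to 3 × 10/7 = 4.3.
- At the daily limit, an upper bound unlikely in an as-needed trial: 7 to 10.

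The gap between tests (7 days) is no longer than the lower end of the interval. So every capsule taken between an opioid dose and the next weekly cup falls inside it.

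Home stock at 3 a week, if the month's 28 are given at once: 28 − 3 = 25, 28 − 6 = 22 and 28 − 9 = 19 after weeks 1, 2 and 3. If the supply is split weekly, 28/4 = 7 per visit. A supply of 28 lasts 28/3 = 9.3 weeks. Declining to dispense more at one visit therefore does not by itself stop dosing.

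These figures count capsules, not men or events.

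**The case against.** The strongest reply is that the protocol has a layered response to opioid use. It has a prohibition, weekly testing, a clinician who dispenses and can discuss medication changes, a pager, a wallet card that alerts outside clinicians, and authority to stop treatment. Few men should be affected, because current users and men with foreseeable opioid need are excluded. Half of those randomized take placebo and face no withdrawal risk. The materials most likely to tell men what to do at home are not visible: the bottle label and its warning statement, the instructional leaflet, the drug administration instructions cited in 8.4.4, the dispenser text and the consent form. Nor are Section 11.3 and a figure in Section 13.

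Most of this stands, and it limits the point. It rules out several stronger readings that a reader might infer:

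- *That the protocol ignores opioid use on treatment.* It does not; the safeguards above are real.
- *That men are told nothing about capsules at home.* That cannot be concluded while those materials are not visible.
- *That opioid use is not among the reasons to stop, because 12.1 does not name it.* Section 12.1 includes protocol violations, and Section 13 names opiate medication as one.
- *That opioid testing ends at baseline, from the Appendix 1 table.* The marks in that table cannot be read reliably, and 9.3.5.1 and 10.4 say weekly.
- *That entry is unprotected.* Criteria 3 and 4 and the 30-day medication history cover it; writing the interval into criterion 3 would be an optional refinement.

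What the reply does not supply is a hold or a restart condition. Discretion at a weekly visit comes after doses may already have been taken, and a pager helps only a man who knows that he should call.

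**Conclusion.** The point holds in a limited form. The visible protocol gives an opioid-free minimum in Section 2.1 but does not turn it into an on-treatment dosing rule. Followed as written, it allows a man with reported opioid use or a positive cup to keep dosing at home and to receive more drug.

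With no hold, the exposure is about 3 to 4 capsules per opioid episode at the encouraged minimum rate, and about 1 at one capsule a week. The documents give no on-study opioid rate, so the number of men affected cannot be estimated; it is probably small, and confined to the 60 assigned to naltrexone. The conclusion rests on the visible text. Confidence is medium because a participant-facing document may already contain part of the rule. The change should be made because the potential harm is serious by the protocol's own account and the remedy is cheap.

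**What to change.** 1. **Section 10.4.** At each weekly visit, read the opioid cup and ask about any new opioid or pain medication before dispensing.
2. **Sections 7.1 and 12.1.** State that reported opioid use or an opioid-positive cup means study drug is held, including capsules at home. The hold lasts until the study clinician confirms a negative opioid urine and 10 opioid-free days, the upper end of the Section 2.1 interval. A hold resting on a cup alone is lifted if the laboratory does not confirm it. Men are already asked to bring their study drug to visits (8.6), so the container can be kept there.
3. **Section 8.4.3.** In the training, tell men to take no capsule after any opioid and to page the study clinician. If the label or leaflet already says this, cross-reference it.

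The rule is identical in both arms, so the blind is kept. Held men remain in follow-up (12.1) and in the intention-to-treat analysis (4.1).

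**Cost.** Amendment wording, one question at an existing visit and one sentence in existing training. No new routine test is needed; a held man may need a repeat cup. Encouraged use over 12 weeks is 3 × 12 = 36 capsules. A full 10-day hold costs 4.3/36 = 11.9% of them; if 3 of the 10 days have already passed when use comes to light, the cost is 3.0/36 = 8.3%. If a full hold waits for the second weekly visit (day 14) instead of a repeat cup at day 10, it costs 3 × 14/7 = 6 capsules (16.7%). The documents give no false-positive rate for the cup, so the number of unnecessary holds cannot be estimated; laboratory confirmation limits their length.

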8 STUDY TREATMENTS

8.1 Method of Assigning Subjects to Treatment Groups

The Better Than Study will enroll 120-participants for the double-blinded placebo controlled trial where 60 eligible participants will be randomly assigned to the treatment group receiving Naltrexone and 60 participants will be randomly assigned to the control group receiving placebo in a 1:1 ratio using a computer-generated randomization scheme developed by our biostatistician. The study biostatistician will generate a random allocation sequence list with treatment assignments associated with order of enrollment, using randomly permuted blocks with randomly selected block sizes.

8.2 Blinding

Due to the objectives of the study, the identity of test and control treatments will not be known to investigators, research staff, or patients. The following study procedures will be in place to ensure double-blind administration of study treatments.

- Access to the randomization code will be strictly controlled.
- Packaging and labeling of test and control treatments will be identical to maintain the blind.

The study blind will be broken on completion of the clinical study and after the study database has been locked.

During the study, the blind may be broken **only** in emergencies when knowledge of the patient's treatment group is necessary for further patient management. When possible, the Investigator should discuss the emergency with the Medical Director prior to unblinding.

Describe the procedures for unblinding.

[figure not shown]
At the end of the study, the biostatistician will provide us with which study drug kits were naltrexone treatment and which study drug kits were placebo. The study drug kits will be compared to the participant enlisted in the study. Study Staff will inform the participant verbally of their study treatment assignment. For those who do not respond by phone, a letter will be sent to their address to inform the participant of their treatment assignment.

8.3 Formulation of Test and Control Products

The Safeway Compounding Pharmacy, which currently prepares our study drug for our ongoing clinical trials, will provide the study drug kits for the proposed trial. Drugs are over-capsuled in a locking capsule to ensure the same appearance across all study arms and maintain double-blind.

Formulation of Test Product

REVIA® (naltrexone hydrochloride tablets USP), an opioid antagonist, is a synthetic congener of oxymorphone with no opioid agonist properties. Naltrexone differs in structure from oxymorphone in that the methyl group on the nitrogen atom is replaced by a cyclopropylmethyl group. REVIA is also related to the potent opioid antagonist, naloxone, or n-allylnoroxymorphone.

REVIA is a white, crystalline compound. The hydrochloride salt is soluble in water to the extent of about 100 mg/mL. REVIA is available in scored film-coated tablets containing 50 mg of naltrexone hydrochloride.

REVIA Tablets also contain: colloidal silicon dioxide, crospovidone, hydroxypropyl methylcellulose, lactose monohydrate, magnesium stearate, microcrystalline cellulose, polyethylene glycol, polysorbate 80, synthetic red iron oxide, synthetic yellow iron oxide and titanium dioxide.

[figure not shown]
8.3.1 Formulation of Control Product

Placebo capsules will contain microcrystalline cellulose (Medisca). Placebo and active medication will be provided in capsules that are an exact match in color, so as to make the placebo and active medication indistinguishable from each other.

8.3.2 Packaging and Labeling

Study drug was initially provided by UCSF Compounding and Research Support Pharmacy, [name]. Since that pharmacy has closed, Safeway Compounding Pharmacy, [name], is used to provide study drug. Each treatment bottle from the UCSF pharmacy was labeled with the study drug number, prescribing physician name (medical director), required FDA warning statement, emergency pager number, directions for participant use and storage, and expiration information. Each treatment bottle from Safeway pharmacy is labeled with the study drug number, principal investigator name, prescribing physician name (medical director), required FDA warning statement, emergency pager number, directions for participant use and storage, and lot and expiration information.

Sample label from UCSF Pharmacy:

8.4 Supply of Study Drug at the Site

Study medication will be supplied to the Center on Substance Use and Health (CSUH) on an as-needed basis, usually 5 or 10 study drug kits at a time. A record of drug receipt will be kept in the investigational drug accountability log. Study drug will be stored in a locked pharmacy with temperature monitoring. Study drug kits provided by the pharmacy will already be randomized, so blinding will be maintained for all staff at the study site.

8.4.1 Dosage/Dosage Regimen

The dose of naltrexone being investigated for potential as a pharmacotherapeutic on an as-needed basis to reduce binge drinking is 50 mg. It is recommended participants take one capsule of medication by mouth 1 to 2 hours before starting an episode of binge drinking. Participants will be instructed to take no more than one capsule in a 24-hour period. No adjustments for weight, age, or meals is required. The dose of naltrexone being investigated for potential as a pharmacotherapeutic on an as-needed basis to reduce binge drinking is 50 mg. It is recommended participants take one capsule of medication by mouth 1 to 2 hours before starting an episode of binge drinking. Participants will be instructed to take no more than one capsule in a 24-hour period. No adjustments for weight, age, or meals is required.

8.4.2 Dispensing

Study medications will be dispensed by the study clinician (licensed medical practitioner) in treatment bottles that are labeled with the study drug number, principal investigator name, prescribing physician name (medical director), required FDA warning statement, emergency pager number, directions for participant use and storage, and lot and expiration information.

Further, at time of study drug dispensing, the study clinician will review with the participant how to take the study medication, possible side effects they may encounter, and how to access the study clinician by emergency pager if necessary. The study clinician will also answer any questions the participant might have.

8.4.3 Administration Instructions

Training on targeted medication dosing:

During enrollment, participants will be trained on medication dosing and be provided a brief instructional leaflet for reference. Participants will be encouraged to intermittently use at least 3 capsules per week, when they believe that drinking is imminent or anticipate a session of binge drinking. At baseline and follow-up visits, study staff will assess each participant's drinking pattern and develop a plan to support intermittent dosing of study drug and maximize medication efficacy. Participants will be given twenty-eight 50 mg tablets per month and will be instructed to not exceed 1 tablet every 24 hours. This dosing is similar to the usual administration of naltrexone for alcohol dependence, except that participants will be taking study drug on an as needed basis instead of daily. Participants will be briefed about the importance of not sharing medications. We will offer participants a wallet card that explains that they may be taking naltrexone. The card provides contact information for medical professionals to seek further information from the study clinician should they have questions.

